9.2.3 Exploratory/Correlative Analysis

The RL algorithm will initially send messages from the three COM-B categories (capability, motivation, opportunity) or no message at random. If a category is predictive of subsequent higher whole grain intake or engagement (responses to text messages), the algorithm will begin to send that type of message more often. We will use one sample tests of proportions to explore if the proportion of text messages sent from each of the three COM-B categories or no message differs from 0.25. For example, for capability messages, our null hypothesis is that the proportion of messages targeting capability is equal to 0.25. The alternative hypothesis is that the proportion of messages targeting capability is not equal to 0.25.

We will also explore whether the distribution of text message type varies by sociodemographic factors (e.g., age, gender, race/ethnicity) using chi-square tests. For example, our null hypothesis is that the distribution of text message type is the same across racial/ethnic groups. The alternative hypothesis is that the distribution of text message type differs across racial/ethnic groups.

10 Study Management

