2.3 Exploratory Objective

Exploratory Objective	Endpoint(s)
Assess convergence of the RL algorithm	Proportion of messages targeting capability, opportunity, or motivation sent during the 12-week period, overall and by sub-groups (e.g., race/ethnicity)

3 Study Design

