We will use the most up-to-date approaches for our RL model. For example, this may include a multi-armed bandit algorithm that predicts the outcome or "reward" (e.g., eating whole grains the previous day [yes/no], or servings of whole grains eaten on the previous day) based on action variables (e.g., whether to send a message, message type) and contextual variables (e.g., individual characteristics, whole grain intake yesterday/past week). RL algorithms "explore" what text messages to send by sending messages randomly at first and then "exploit" the information, so that over time, the algorithm sends more of the messages that predict more frequent intake of whole grains. In our proposal, participants' replies to daily text messages asking about their intake of whole grains on the previous day will be used as the "reward" data.

Participants' response rate to the daily question about whole grain intake is a primary outcome in this study. We will send a reminder message to participants who have not responded (e.g., "Please respond even if you ate 0 whole grains yesterday.") If participants do not respond a few days in a row, we will send a non-response message (e.g., "We haven't heard from you in a few days. Please respond to the text messages or contact our team at [study phone number].") If a participant does not respond for 7 consecutive days, we may invite them to a semi-structured

interview to understand reasons for non-response. Non-responders will continue to receive study text messages unless they request the messages be stopped (e.g., by texting back STOP or notifying the study team). All participants, including non-responders, will be asked to complete the surveys at 12 weeks to gather quantitative usability and acceptability data and estimate the effect of the intervention on diet behavior.

Educational material

At enrollment, all participants will receive printed materials defining the recommendations for whole grain intake, what is a whole grain, whole grain serving sizes, and cooking tips.

Intervention Components for Food Insecure Participants

We will use the Food Security module from the National Health Interview Survey to identify food insecure participants at enrollment. We will follow the standard of care at ZSFG for food insecure individuals: the study coordinator will provide a list of resources including food banks and meal delivery programs and facilitate application or SNAP benefits, if needed.

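### Section 9.2.3 tests adaptively chosen messages, clustered within participants, as if they were independent draws, so its p-values do not show that the algorithm learned from a real signal

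*Combined protocol and SAP*

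**What the plan says.** Section 2.3 sets an exploratory objective, convergence of the reinforcement learning algorithm, with one listed endpoint: "Proportion of messages targeting capability, opportunity, or motivation sent during the 12-week period", overall and by subgroup.

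Section 9.2.3 describes random sending at first. If a category is "predictive of subsequent higher whole grain intake or engagement (responses to text messages"), then "the algorithm will begin to send that type of message more often". The analysis is stated as "We will use one sample tests of proportions to explore if the proportion of text messages sent from each of the three COM-B categories"; the full comparison is whether the share for "each of the three COM-B categories or no message differs from 0.25", with a two-sided alternative. For subgroups: "We will also explore whether the distribution of text message type varies by sociodemographic factors", by chi-square tests.

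Section 5 leaves the algorithm open: "For example, this may include a multi-armed bandit algorithm that predicts the outcome". Its contextual inputs may include "individual characteristics, whole grain intake yesterday/past week", and the opening of section 5 lists sociodemographic characteristics among the factors that may drive adaptation. The length of the random phase, and whether learning is shared between participants, are not stated. Neither section 9.2.3 nor any other section mentions clustering within participant, dependence of sends on earlier outcomes, or a no-effect reference for the algorithm.

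**The concern.** A one-sample proportion test and a contingency-table chi-square both take their null variance from independent draws with fixed probabilities. Messages here are neither. Each participant contributes many of them, and the probability of each category changes in response to earlier replies. Early chance results feed into later choices, so shares spread far beyond binomial variation even when every category works equally well.

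These shares are the only listed endpoint for the objective in section 2.3. A small p-value could be taken to mean that the algorithm found a better category, or found different needs by race/ethnicity, age or gender, when chance feedback alone can produce it. The results are meant to inform a later randomized trial (section 1.4).

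**Working it through.** **1. The plan's own figure.** Three categories plus no message, sent uniformly, give 1/4 = 0.25. This reproduces. It holds only if no-message decisions are in the denominator. If only messages sent are counted, as section 2.3 reads, uniform sending gives 0.25/0.75 = 1/3.

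**2. What the named test assumes.** Inputs: 60 participants (section 3.3) and 12 weeks = 84 days (section 5). Assumed: one decision per person per day, and a 5% level, since section 9.2.3 gives none.
- Decisions: 60 × 84 = 5,040.
- SE = √(0.25 × 0.75 / 5,040) = 0.0061.
- The test rejects outside 0.25 ± 1.96 × 0.0061, that is 0.238 to 0.262.

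**3. Cost of mixing denominators.** Under uniform sending about 0.75 × 5,040 = 3,780 messages are sent and each category's share is 1/3. Tested against 0.25, z = (0.3333 − 0.25) / √(0.1875 / 3,780) = 0.0833 / 0.0070 ≈ 11.8. Purely random sending would be rejected.

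**4. Clustering alone.** Design effect = 1 + (84 − 1) × ICC. An ICC of 0.01 gives 1.83 and a true type I error of 15%; 0.05 gives 5.15 and 39%; 0.10 gives 9.3 and 52%. Simulated person-level learners had ICCs of about 0.07 to 0.31.

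**5. Adaptive sending with nothing to learn.** Assumed, not in the documents: reward probability 0.5 for every option, 70% of rewards observed, 14 random days, four groups of 15, updating at the end of each day, and entry spread over about 640 days (roughly 24 months less 12 weeks). There were 1,000 trials per setting. Cells show rejections at nominal 5%: single share test / subgroup chi-square (4 × 4, 9 df).

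| Algorithm | Person-level | Group-level | Pooled |
|---|---|---|---|
| Thompson | 54.6 / 99.6% | 87.9 / 100% | 94.4 / 87.0% |
| UCB1 | 24.5 / 74.6% | 68.4 / 100% | 83.4 / 89.8% |
| Epsilon-greedy | 70.3 / 100% | 88.9 / 100% | 97.5 / 85.2% |

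Random sending throughout gave 5.3 / 4.5%, so adaptive sending causes the excess. A separate Thompson run with simultaneous entry (400 trials) gave 54%, 86% and 94% for the share test, against 5.8% with random sending.

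**6. Check by hand.** The Thompson share had SD 0.020 (person), 0.070 (group) and 0.137 (pooled), against 0.006 binomial. If the share is roughly normal around 0.25, the rejection rate is 2 × [1 − Φ(0.012 / SD)]: 55%, 86% and 93%, close to the simulated values.

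**7. When the chi-square is not inflated.** One pooled learner with simultaneous entry gave 3.5% (Thompson), 0% (UCB1) and 0.7% (epsilon-greedy). Two conditions are needed.
- Entry: pooled Thompson rose to 10.5% with entry over 30 days, 41% over 90 and 87% over 640.
- Inputs: for a pooled linear Thompson learner with simultaneous entry (200 trials), the chi-square rejected 2% without demographic context and 100% with a group-by-action term.

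**8. Sensitivity.** With person-level learning (500 trials), a minimum probability of 0.10, 0.15 or 0.20 per option cut the share test to 35%, 23% and 10%, and the chi-square to 92%, 62% and 19%. A 56-day random phase gave 26% and 72%. The inflation shrinks but remains.

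**9. What restores size.**
- A one-sample t-test on 60 participants' shares rejected in 5–6% when each participant had a separate learner (2.8% in another run). It rejected in 65–67% with group-shared and 94–99% with pooled learning.
- A reference from re-running the same algorithm with no effect gave about 5–6% when intake did not change over time. With a pooled learner and an assumed linear rise in intake of 10 or 20 points, a constant-rate reference gave 16.8% or 35.8% for the shares; adding a time trend brought these to 3.5% and 3.0%. Person-level share tests did not need the trend (5.0–5.2% with constant rates). Only linear changes were tried.

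**The case against.** **The analysis is exploratory.** This stands. No feasibility or acceptability criterion in sections 2.1 or 9.1.1 uses it, which limits the severity.

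**The stated null concerns only whether a share differs from 0.25.** Read literally, a rejection may correctly report that sending left uniform, or differed between groups, in this trial. That much stands. Convergence can also mean that allocation settled, even on a category that is no better. The plan does not say that a small p-value will be presented as proof of learning; a reader might infer that intention, but the text does not state it. The defect is that the p-value comes from a null distribution that does not apply and cannot separate learning from drift.

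**The algorithm is not specified, so no error rate can be computed.** This also stands. A reader might take the simulated rates as this trial's false-positive rates or as limits on them. They are neither: forced exploration or a longer random phase lowers them. Still, the share test was inflated in every adaptive setting tried.

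**A cluster adjustment would be enough.** Only with separate learners. Under pooled learning the within-participant ICC is near zero, yet the participant-level t-test still rejects in 94–99%.

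**A pooled learner protects the subgroup test.** Only if it ignores demographics and participants start together. Section 5 permits demographic inputs, and section 3.4 allows 24 months to primary completion, so neither condition can be presumed.

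**Conclusion.** The point holds and should be fixed, at modest severity. The tests named in section 9.2.3 are not calibrated for outcome-dependent, clustered sends. With no category better than another, illustrative Thompson runs reject 0.25 in about 54% (person-level), 86–88% (group-level) and 94% (pooled) of trials at nominal 5%, against about 5% with random sending. The subgroup chi-square rejects in about 100% of these Thompson runs with person-level or group-level learning.

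Confidence is high in the diagnosis. The sizes depend on the assumed algorithm, random phase, decisions per day, reply rate and accrual pattern.

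Two stronger readings go too far. One is that the subgroup chi-square is inflated under every design; the pooled, demographics-blind, simultaneous-entry case is an exception. The other is that the trial's main conclusions are at risk; nothing in the feasibility, acceptability or dietary analyses rests on these tests.

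The mismatch between three categories in section 2.3 and four options in section 9.2.3 is a smaller, separate point that needs no simulation.

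**What to change.** In section 9.2.3:

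1. **Main change.** Drop the binomial and chi-square p-values for message shares. Report shares descriptively per participant and over time (random phase, later weeks, full 12 weeks), overall and by subgroup. State that a share different from 0.25 is not by itself evidence of learning.
2. **Only if p-values are kept.** With a separate learner per participant, use participant-level tests, such as a one-sample t-test of participants' shares against 0.25 and participant-level subgroup comparisons. With pooled or group-shared learning, take the reference distribution from re-running the documented algorithm with actual entry dates and no action effect. Keep each participant's level and the time trend, and regenerate any context built from past rewards within each re-run.
3. **Denominator.** Reconcile sections 2.3 and 9.2.3: 0.25 if decision points including no message are counted, or 1/3 if only messages sent are counted.

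Items 1 and 3 are wording only and need no new data. Item 2 needs simulation code, and a documented algorithm with its version changes, only where learning is shared. The price is fewer nominally significant exploratory results.

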4.4.2 Study Design/Recruitment Considerations Related to Age Groups

Individuals ages 18 and over are eligible for this study. We will strive to enroll people who represent the age distribution of individuals affected by CRC. However, given the rapidly rising incidence of CRC among people <50 years old, we may over-enroll people <50 years compared to the distribution of cases in the overall population. This will ensure our results are useful for guiding CRC survivorship care for an increasing population of younger and middle-aged adults.

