4.6 Assignment to Intervention

This is a single-arm study. All participants will receive the 12-week adaptive text message intervention.

5 Study Intervention

We aim to develop a dietary intervention that will continuously adapt text message content and timing based on factors that may include: participants' sociodemographic characteristics, dietary behavior, and engagement with the text messages.

Our theoretical framework is based on the Capability Opportunity Motivation-Behavior (COM-B) model which states that individuals' behaviors are the result of interactions between their capabilities, opportunities, and motivations. Applying the model to whole grain intake, CRC survivors must have:

- 1) capability – the physical ability to consume whole grains without side effects (e.g., gas, bloating, bowel frequency); knowledge and skills to select and prepare whole grains; and psychological capability to resist cravings and control urges for refined grains;
- 2) opportunity – whole grains must be available, affordable, and socially acceptable; and
- 3) motivation – motivated to eat whole grains and develop a plan for doing so.

Intervention Components

Adaptive text messages using reinforcement learning (RL)

After completing baseline assessments, all participants will receive text messages for 12 weeks. Most days, participants will receive 1-2 messages. Text messages will be sent through the HealthySMS Platform and Twilio. Message content will target COM-B components of capability, opportunities, and motivations. The RL model will use a bank of text messages to target COM-B constructs. For example, to address psychological capability, messages will increase knowledge of what foods are recommended and how to prepare them. Behavior change techniques will include providing information, feedback, self-monitoring, and prompts/cues to increase knowledge. To address physical opportunity, text messages will focus on how to economically shop for and prepare whole grain foods. Behavior change techniques will include restructuring the physical environment, prompts/cues, instruction, feedback, and self-monitoring.

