9.1 Sample Size Considerations

9.1.1 Sample Size and Power Estimate

Sample size: up to 60.

We will consider our study to the median response proportion to text messages that ask for a reply is $\geq 70\%$, and the median Feasibility of Intervention Measure score is 4 or higher. The intervention will be determined acceptable if median scores on the Acceptability of Intervention and Intervention Appropriateness Measures are ≥ 4 . With our sample size of 60 participants and assuming a standard deviation (SD) for the mean text message response rate of 25% based on prior work,¹⁰ we will be able to detect an average text message response rate of 70% with a 95% CI of 64%-76%.³³

For our secondary outcome of percent of grains that are whole, using a paired t-test to compare mean proportion of total grains that are whole at 0 and 12 weeks, alpha=0.05, a SD=23% for the mean change in proportion of grains that are whole,¹⁰ 20% drop out, and 60 participants, we will have 80% power to detect a $\geq 9\%$ change in proportion of grains that are whole.³⁴

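### Section 9.2.3 tests age by chi-square on age groups it never defines; a regression on age in years with the participant as the unit is a cheap improvement to this exploratory analysis

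*Combined protocol and SAP*

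**What the plan says.** The exploratory endpoint in Section 2.3 is "Proportion of messages targeting capability, opportunity, or motivation sent during the 12-week period, overall and by sub-groups". Section 9.2.3 then sets out two analyses. The first asks if the "proportion of text messages sent from each of the three COM-B categories or no message differs from 0.25". The second concerns participant characteristics: "We will also explore whether the distribution of text message type varies by sociodemographic factors (e.g., age, gender, race/ethnicity) using chi-square tests". The worked example for the second is that "our null hypothesis is that the distribution of text message type is the same across racial/ethnic groups".

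No age groups are defined in Section 9.2.3 or elsewhere. Apart from the entry age, the only age boundary in the document is 50 years, in Section 4.4.2, where it concerns recruitment: "we may over-enroll people <50 years compared to the distribution of cases in the overall population". Section 9.2.3 states no alpha, effect size or power for these tests and describes no step for repeated messages from the same person.

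**The concern.** Gender and race/ethnicity are categories; age is not. Applying one contingency-table test to all three has three consequences for age.

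- Age has to be cut. With no cut-points in the plan, the grouping can be chosen after the message data have been seen.
- A Pearson chi-square treats the groups as unordered, so a steady trend with age is tested as if any pattern were equally plausible.
- The thing compared is a distribution of messages. Up to 60 people contribute thousands of messages, and messages to one person from an adaptive algorithm are unlikely to be independent.

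Section 5 says that adaptation may depend on sociodemographic characteristics, so whether the message mix differs by age is a sensible exploratory question, and Section 1.4 says the results will inform a later randomized trial. What is at stake is whether an age finding, positive or negative, can be believed.

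**Working it through.** **No plan figure to reproduce.** The document gives no power or effect size for this analysis, so the check shows what grouping and pooling do under stated assumptions.

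**Inputs from the document.** Sample: "Sample size: up to 60" (Section 9.1.1). Duration: "all participants will receive text messages for 12 weeks" (Section 5), that is 12 × 7 = 84 days. Frequency: "Most days, participants will receive 1-2 messages" (Section 5). Starting share of each option: 0.25 (Section 9.2.3).

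**Assumptions, not in the document.** One send decision per person per day (60 × 84 = 5,040 decisions); age normal with mean 58 and SD 12, so about 25% are under 50; an age effect linear on the logit scale; between-person SD 0.5 on the logit scale; two-sided 0.05; one message type examined.

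**Step 1: participant as the unit, analytic check.** Power for a correlation r between age and a participant's share is Φ(atanh(r)·√(n−3) − 1.96). With n = 60, √57 = 7.55. Splitting normal age at proportion p multiplies r by φ(z_p)/√(p(1−p)), which is 0.798 for a median split and 0.734 for a 25/75 split.

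- Continuous, r = 0.355: 0.371 × 7.55 − 1.96 = 0.84, power 80%.
- Median split, r = 0.355 × 0.798 = 0.283: 0.291 × 7.55 − 1.96 = 0.24, power 59%, a loss of 21 points.
- 25/75 split, r = 0.355 × 0.734 = 0.261: 0.267 × 7.55 − 1.96 = 0.05, power 52%, a loss of 28 points.
- Starting from 30% instead (r = 0.188), the same splits give 21% and 18%, losses of 9 and 12 points.

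**Step 2: participant as the unit, simulation.** Tests on the 60 participant-level shares: correlation with age, t-tests for two groups, one-way ANOVA for three or four. Effects are in logits per SD of age; 20,000 replicates per row.

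| Effect | Age in years | Median split | <50 cut | Tertiles | Quartiles |
|---|---|---|---|---|---|
| 0 | 4.9% | 5.0% | 5.2% | 5.0% | 5.1% |
| 0.15 | 51% | 35% | 28% | 32% | 30% |
| 0.22 | 82% | 62% | 52% | 61% | 58% |
| 0.25 | 90% | 72% | 62% | 72% | 69% |

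At 0.22 the losses are 82 − 62 = 20 to 82 − 52 = 30 points. At a smaller effect of 0.10 (4,000 replicates), age in years has 27%, the median split 19% and the <50 cut 14%: losses of 8 and 13 points. The loss also moves with the between-person SD. At SD 0.25 it is about 17-28 points for effect 0.15 but only 2-7 for effect 0.25; at SD 1.0 it is about 6-20 points.

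**Step 3: messages pooled, as the text reads.** A pooled chi-square takes the variance of a person's share to be p(1−p)/84 = 0.1875/84 = 0.00223. Between-person variation adds about (0.1875 × 0.5)² = 0.00879. The true variance is therefore about (0.00223 + 0.00879)/0.00223 = 4.94 times what the test assumes, and √4.94 = 2.22. With no age effect, the false-positive rate is about 2 × [1 − Φ(1.96/2.22)] = 2 × [1 − Φ(0.88)] = 38%. Simulation with a median age split also gives 38%. At effects 0.15 and 0.22 the pooled test rejects 77% and 92% of the time.

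With all four message options and two age groups, the simulated false-positive rate is 34%, 72% and 94% for between-person SDs of 0.25, 0.5 and 1.0. Using age in years on pooled messages does not help (36%, 72%, 93%); participant-level tests stay near 5%.

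**Step 4: if the age effect is not linear.** With a step at age 50 of 0.5 logit, participant-level power is about 48% for age in years and 79% for the <50 split. With a step of 0.4 it is 35% and 60%.

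**The case against.** The strongest reply is that little depends on this. The analysis is exploratory, age is given only as an example, no power is claimed for it, and the endpoint in Section 2.3 is itself defined by sub-groups, so grouping fits the plan. All of that stands, and it limits the point to a minor improvement.

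Two stronger readings are tempting, and the documents do not support either.

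- A reader might infer that the chi-square test costs a fixed 20 to 30 points of power. That range belongs to one part of the assumed effect range, with participants as the unit. Effect size, age distribution and between-person SD are all assumed, and the loss is smaller at weak effects and at very strong ones.
- A reader might infer that a real age difference will probably be missed. The text compares message distributions and describes no participant-level test. Pooled, its main risk is an age difference that is not there.

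Nor does Section 4.4.2 make an age gradient in message type a study question. It concerns who is recruited and how useful the results are for younger survivors.

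It is also fair to say that a linear simulation favours continuous age by construction. Step 4 shows the reverse when the effect is a step at 50, the one boundary the document names. That objection stands and shapes the remedy.

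**Conclusion.** The concern holds in limited form. Section 9.2.3 assigns age a test that needs groups, defines none, ignores their order and, as worded, treats messages as independent.

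With participants as the unit and a roughly linear effect, grouping costs about 8-13 points of power when continuous age would have about 27%, and about 20-30 points when it would have about 80%. With messages pooled, the age test rejects about 38% of the time under no age effect, for one message type, a median split and a logit SD of 0.5. Every size here rests on the assumptions listed in the working; the document supplies only the sample size, the message period and frequency, and the 0.25 starting share.

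No stated design property is broken and no primary or secondary endpoint is touched. This is a cheap improvement, not a flaw that threatens the trial.

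**What to change.** In Section 9.2.3:

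- Limit the chi-square wording to categorical factors.
- For age, regress each participant's share of each message type on age in years, or fit a multinomial model of message type with participant-clustered standard errors (an option not simulated here). Report the slopes with 95% CIs, all of them, as exploratory.
- Check linearity with a plot.
- Report the <50 versus ≥50 difference with a participant-level 95% CI as a supporting contrast, named in advance.

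The cost is a sentence or two in the plan and one regression. Age has to be known for eligibility and is among the items in the Section 6.2.1 record review, so nothing further is collected. The downside is the linearity assumption: if the effect is a step at 50, the slope has less power than the split (about 48% against 79% at a step of 0.5 logit), which is why the contrast should carry an interval and not be only a descriptive table.

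Gender and race/ethnicity also need participant-level handling, since restricting chi-square to them leaves the pooling problem in place. That is a separate point.
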